## LIST OF ABBREVIATIONS

AE	adverse event
ATC	Anatomical-Therapeutic-Chemical (drug coding system)
AUC	area under the curve
AUC 0-12	area under the curve for 0 – 12 hours
AUC 0-last	area under the curve for 0 – last sampling time point
BID	twice a day
BMI	body mass index
BOR	best overall response
CI	confidence interval
CR	complete response
CRF	case report form
C max	maximum plasma concentration
CSR	clinical study report
CT	computerized tomography
CTCAE	Common Terminology Criteria for Adverse Events
C trough	trough drug concentration
DNA	deoxyribonucleic Acid
DOR	duration of response
ECG	electrocardiogram
ECOG	Eastern Cooperative Oncology Group
FACT-Lym	Functional Assessment of Cancer Therapy: Lymphoma
FDG	fluorodeoxyglucose
FL	follicular lymphoma
HLGT	high-level group term
HLT	high-level term
HRQL	health-related quality of life
ICH	International Conference on Harmonisation
iNHL	indolent Non-Hodgkin lymphoma
IRC	independent review committee
ITT	intent-to-treat
IWRS	interactive web response system
LLQ	lower limit of quantification
LLT	low level term
LPL	lymphoplasmacytoid lymphoma
MedDRA	Medical Dictionary for Regulatory Activities
MMRM	mixed-effects model repeated measures
MRI	magnetic resonance imaging
MZL	marginal zone lymphoma
ND	no disease

---

NE	not evaluable
NHL	non-Hodgkin lymphoma
ORR	overall response rate
OS	overall survival
PD	progressive disease
PET	positron-emission tomography
PFS	progression-free survival
PK	pharmacokinetic
PP	per protocol
PR	partial response
PT	preferred term
QTc	QT interval corrected
QTc-B	QT interval corrected for heart rate using Bazett's formula
QTc-F	QT interval corrected for heart rate using Fridericia's formula
SAE	serious adverse event
SAP	statistical analysis plan
SD	stable disease
SE	standard error
SLL	small lymphocytic lymphoma
StD	standard deviation
SOC	system organ class
SPD	sum of the products of the perpendicular diameters of measurable index lesions
SPEP	serum protein electrophoresis
$t_{1/2}$	half-life
TEAE	treatment-emergent adverse event
$T_{max}$	time of maximum concentration
TTR	time to response
WHODRUG	World Health Organization Drug Classification Dictionary

## 1. INTRODUCTION

This statistical analysis plan (SAP) describes the analyses to be conducted for Gilead Sciences, Inc. idelalisib (IDELA) Study 101-09. The final study analysis will be performed when all enrolled subjects have completed efficacy, safety, and other assessments through  $\geq 24$  weeks of evaluation.

### 1.1. Study Objectives

Primary Study Objectives	

• To evaluate tumor regression as determined by overall response rate (ORR) in subjects receiving IDELA for treatment of iNHL refractory to rituximab and alkylating agents

Secondary Study Objectives	

• To determine the onset, magnitude, and duration of tumor control and of treatment success in subjects receiving IDELA

• To characterize health-related quality of life (HRQL) as reported by subjects with iNHL receiving IDELA

• To evaluate the effects of IDELA on subject performance status

• To assess the pharmacodynamic effects of IDELA

• To evaluate IDELA treatment administration and compliance with IDELA therapy

• To describe the safety profile of IDELA

• To characterize IDELA plasma exposure over time

## 1.2. Study Design

Design Configuration and Subject Population	
This protocol describes a Phase 2, open-label, single-arm, 2-stage, efficacy, safety, and pharmacodynamic study of IDELA in subjects with previously treated iNHL that is refractory both to rituximab and to alkylating-agent-containing chemotherapy.
 
Eligible subjects will initiate oral therapy with IDELA at a starting dose of 150 mg BID given continuously. Treatment with IDELA will continue until tumor progression or unacceptable toxicity. Subjects will be followed in the clinic at 2-week intervals through the first 12 weeks of treatment, at 4-week intervals from 12 to 24 weeks of treatment, at 6-week intervals from 24 to 48 weeks of treatment, and at 12-week intervals thereafter. Tumor response will be evaluated at baseline; at 8, 16, and 24 weeks of therapy; and every 12 weeks thereafter according to standard criteria. The responses will be assessed by both the investigator and an independent review committee (IRC).
 
The study will be conducted in 2 stages using Simon's optimal 2-stage design. In Stage 1 of the study, 31 subjects will be enrolled; if <math>\geq 9</math> of these Stage 1 subjects have a tumor response, then the study will continue. In Stage 2, a further 69 subjects will be enrolled. With a total intended sample size of 100 subjects, the study has power <math>>0.90</math> to achieve a 1-sided significance level of 0.005 and will provide an ample safety database.

Treatment Groups	
Starting Dose: 150 mg BID
 
Reduced Dose -1: 100 mg, BID
 
Reduced Dose -2: 75 mg, BID

Key Eligibility Criteria	
	

• Age <math>\geq</math> 18 years

• Karnofsky performance score <math>\geq</math> 60 (Eastern Cooperative Oncology Group [ECOG] performance score of 0, 1, or 2)

• Histologically confirmed diagnosis of B-cell iNHL, with histological subtype limited to the following based on criteria established by the World Health Organization (WHO) 2008 classification of tumors of haematopoietic and lymphoid tissues:

— Follicular lymphoma (FL) Grade 1, 2, or 3a

— Small lymphocytic lymphoma (SLL) with absolute lymphocyte count <math><5 \times 10^9/L</math> at the time of diagnosis and on baseline laboratory assessment performed within 4 weeks prior to the start of study drug administration

— Lymphoplasmacytic lymphoma/Waldenstrom Macroglobulinemia (LPL/WM)

— Marginal zone lymphoma (MZL) (splenic, nodal, or extra-nodal)

• Histological materials documenting diagnosis of lymphoma available for review. Note: Central pathology confirmation of diagnosis will be performed in this study. However, a subject may be enrolled without waiting for confirmation of histological diagnosis on condition that pathological materials are known to be available for review.

• Presence of radiographically measurable lymphadenopathy or extranodal lymphoid malignancy (defined as the presence of <math>\geq 1</math> lesion that measures <math>\geq 2.0</math> cm in the longest dimension [LD] and <math>\geq 1.0</math> cm in the longest perpendicular dimension [LPD] as assessed by <math>\geq</math> CT or magnetic resonance imaging [MRI])

• Prior treatment with <math>\geq 2</math> chemotherapy- or immunotherapy-based regimens, or with rituximab/with an alkylating agent for iNHL

• Prior treatment with rituximab and with an alkylating agent (eg, bendamustine, cyclophosphamide, ifosfamide, chlorambucil, melphalan, busulfan, nitrosoureas) for iNHL.

• Lymphoma that is refractory to rituximab and to an alkylating agent

	

• Refractoriness is defined as:

•  Rituximab (without chemotherapy):

— Lack of a complete response (CR) or partial response (PR) during rituximab therapy comprising <math>\geq 4</math> doses of <math>\geq 375</math> mg/m^2 given weekly, or

— Occurrence of progressive disease (PD) within 6 months of the completion of a regimen of rituximab therapy comprising <math>\geq 4</math> doses of <math>\geq 375</math> mg/m^2 given weekly, or

— Occurrence of PD during rituximab maintenance therapy or within 6 months of completion of rituximab maintenance therapy

• Rituximab (with chemotherapy):

— Lack of a CR or PR during rituximab-containing therapy comprising <math>\geq 2</math> doses of <math>\geq 375</math> mg/m^2, or

— Occurrence of PD within 6 months of the completion of a regimen of rituximab-containing therapy comprising <math>\geq 2</math> doses of <math>\geq 375</math> mg/m^2, or

— Occurrence of PD during rituximab maintenance therapy or within 6 months of completion of rituximab maintenance therapy

• Alkylating agent (administered with or without rituximab):

— Lack of a CR or PR during alkylating-agent-containing therapy comprising <math>\geq 2</math> cycles of treatment, or

— Occurrence of PD within 6 months of the completion of a regimen of alkylatingagent-containing chemotherapy comprising <math>\geq 2</math> cycles of treatment

• Discontinuation of all other therapies for the treatment of iNHL <math>\geq 3</math> weeks before initiation of study treatment (Visit 2).

• All acute toxic effects of any prior antitumor therapy resolved to Grade <math>\leq 1</math> before initiation of study treatment (Visit 2) (with the exception of alopecia [Grade <math>\leq 2</math> permitted], neurotoxicity [Grade <math>\leq 2</math> permitted], or bone marrow parameters noted in Table 1 [Grade <math>\leq 2</math> permitted]).

• Required baseline laboratory data (within 4 weeks prior to start of study drug administration) as shown in Table 1 of the study protocol.

--	--

Study Periods/Phases	
This study will consist of 3 study periods. The screening period will be 4 weeks or less. The treatment period may continue until the occurrence of any events requiring treatment discontinuation. The long-term post-treatment follow-up period will be from the last dose of study drug up to Year 5.
 
The study will be conducted in 2 stages using Simon's optimal 2-stage design. In Stage 1 of the study, 31 subjects will be enrolled; if <math>\geq 9</math> of these Stage 1 subjects have a tumor response, then the study will continue. In Stage 2, a further 69 subjects will be enrolled. The final study analysis will be performed when all enrolled subjects have completed efficacy, safety, and other assessments through at least 24 weeks of evaluation.

-----------------------------	---

### Schedule of Assessments

Period	Screen	Treatment															Follow-up		
Visit	1	2	3	4	5	6	7	8	9	10	11	12	13	14	15	16+	End of Treatment	Immediate post-treatment	Long-term
Week	-4	0	2	4	6	8	10	12	16	20	24	30	36	42	48	Q12 Weeks			
Study Day	Within -28 Days	1	15	29	43	57	71	85	113	141	169	211	253	295	337				
Visit Window		±2	±2	±2	±2	±2	±2	±2	±3	±3	±3	±3	±3	±7	±7	±7			
Informed consent	X																		
Medical history	X																		
Histopathology review	X																		
Serum virology	X																		
Coagulation	X																		
Urinalysis	X																		
β-HCG	X																		
PPD																			
HRQL – FACT-Lym		X		X		X		X	X	X	X	X	X	X	X				
Study drug return/accounting			X		X		X	X	X	X		X		X	X	X			
Adverse events		X		X		X		X	X	X	X	X	X	X	X	X	X		
Concomitant medications	X	X		X		X		X	X	X	X	X	X	X	X	X			
Performance status	X	X		X		X		X	X	X	X	X	X	X	X	X			
Vital signs	X	X		X		X		X	X	X	X	X	X	X	X	X			
Hematology	X	X	X	X	X	X	X	X	X	X	X	X	X	X	X	X			
Serum chemistry	X	X	X	X	X	X	X	X	X	X	X	X	X	X	X	X			
Pharmacodynamics		X		X		X		X	X	X	X	X	X	X	X	X			
Drug dispensing		X		X		X		X	X	X	X	X	X	X	X	X			

Period	Screen	Treatment																Follow-up		
		1	2	3	4	5	6	7	8	9	10	11	12	13	14	15	16+	Q12 Weeks	End of Treatment	Imme- di- ate post- treat- ment
Visit	1																			
Week	-4	0	2	4	6	8	10	12	16	20	24	30	36	42	48					
Study Day	Within -28 Days	1	15	29	43	57	71	85	113	141	169	211	253	295	337					
Visit Window			±2	±2	±2	±2	±2	±2	±3	±3	±3	±3	±3	±7	±7	±7				
Physical examination	X								X									X		
12-lead ECG	X								X									X		
Immunophenotyping		X				X			X		X		X		X	X	X			
Serum immunoglobulins		X				X			X		X		X		X	X	X			
Radiology assessments (CT/MRI)	X					X			X		X		X		X	X	X			
Bone marrow biopsy/aspirate a	X					X a			X a		X a		X a		X a	X a				
SPEP (IgM monoclonal protein)	X					X			X		X		X		X	X	X			
Idelalisib dosing in clinic		X		X		X			X											
Limited PK		X		X		X			X											
PPD																				

#### Study Procedures and Timingc

a Required at screening. If disease present at baseline, to be performed post-baseline to confirm response category in subjects with potential CR by radiological assessments. If the baseline bone marrow biopsy/aspirate does not show lymphoma involvement, it is not necessary to obtain a follow-up bone marrow biopsy/aspirate to establish CR.

b For subjects with LPL only, performed locally per standard of care

c For detailed information regarding activities to be performed at each visit, see Section 7.2 of study 101-09 protocol.

**Abbreviations:** β-HCG, beta human chorionic gonadotropin; HRQL, health-related quality of life; FACT-Lym, Functional Assessment of Cancer Therapy- Lymphoma; ECG, electrocardiogram; CT, computed tomography; LPL, lymphoplasmacytoid lymphoma; MRI, magnetic resonance imaging; SPEP, serum protein electrophoresis; CR, complete response

Randomization	No randomization will be performed in the study.
Site and/or Stratum Enrollment Limits	
Study subjects will be enrolled at investigational sites in North America and Europe.
 
At least 50 subjects with prior bendamustine exposure will be enrolled. The IWRS will gate accrual of subjects without prior bendamustine treatment.

Study Duration	
All subjects may receive study drug indefinitely unless any of the withdrawal criteria (such as withdrawal of consent, experienced an adverse event, or tumor progression) indicated in Section 9 of the protocol is met.
 
Subjects will be followed in the clinic at 2-week intervals through the first 12 weeks of treatment, at 4-week intervals from 12 to 24 weeks of treatment, at 6-week intervals from 24 to 48 weeks of treatment, and at 12-week intervals thereafter. Tumor response will be evaluated at baseline; at 8, 16, and 24 weeks of therapy; and every 12 weeks thereafter according to standard criteria. The responses will be assessed by both the investigator and an independent review committee (IRC), with the IRC-reviewed responses treated as primary in the efficacy analyses.
 
Enrollment is planned to occur over <math>\leq</math> 15 months; subject follow-up will continue through <math>\geq</math> 6 months.

### 1.3. Sample Size and Power

Planned Sample Size	Up to 120 subjects may be enrolled in order to ensure enrollment of $\geq$ 100 subjects (31 in Stage 1, and 69 in Stage 2) who have a documented diagnosis of lymphoma, who have confirmed refractory disease, and who can be evaluated for tumor response with baseline and on-study scans (through the planned 24-week, follow-up tumor assessment).
Power Statement	The null hypothesis that the IRC-reviewed ORR is $\leq$ 20% will be tested against the alternative hypothesis that it is $\geq$ 39% (ie, $\sim$ 40%). Using Simon's optimal 2-stage design [Simon 1989], a sample size of 100 subjects has power $>$ 0.90 to achieve a 1-sided significance level of $<$ 0.005 and will provide an adequate safety database.
Actual Enrollment and Impact on Power	A total of 125 subjects have been enrolled into this study and this will provide $>$ 0.90 power to test the primary hypothesis.

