## **2. TYPE OF PLANNED ANALYSIS**

### **2.1. Interim Analysis**

A single formal interim analysis is planned under Simon's optimal 2-stage design. The sole purpose of this interim analysis is to determine if there is a sufficient ORR observed early in the study to warrant continuing the study to completion. The interim analysis constitutes a futility analysis; it will not be used to stop the trial early for positive efficacy.

In Stage 1 of the study, 31 subjects will be enrolled. If  $\geq 9$  Stage 1 subjects have a response (ie, complete response or partial response), then the study will continue. If  $< 9$  Stage 1 subjects have a response, accrual to the study will be halted. At the end of Stage 1, the probability of erroneously proceeding with the study is 0.151 under the null hypothesis and of erroneously discontinuing the study is 0.091 under the alternative hypothesis.

If the required Stage 1 tumor ORR is seen based on investigator assessments, accrual can proceed in Stage 2 without interruption. If the required total number of subjects are accrued to Stage 1 but follow-up is not sufficiently mature (ie, through the Week 16 radiographic evaluation) in all Stage 1 subjects to reasonably assess the Stage 1 ORR, accrual to Stage 2 may proceed while the Stage 1 data are being collated. All available tumor response and progression data will be considered at the time of the assessment. At the latest, the interim analysis will be performed when the last of the Stage 1 subjects has been enrolled and has completed the 16-week tumor assessment and these data are evaluated.

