### **2.2. Final Analysis**

In Stage 2 of the study, it is planned that 69 subjects will be enrolled to achieve the total intended sample size of 100 subjects. The final study analysis will be performed when all enrolled subjects have completed efficacy, safety, and other assessments through at least 24 weeks of evaluation.

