### **3. GENERAL CONSIDERATIONS FOR DATA ANALYSES**

#### **3.1. Analysis Sets**

##### **3.1.1. Intent-to-Treat Analysis Set**

The intent-to-treat (ITT) analysis set will comprise all subjects who receive  $\geq 1$  dose of IDELA. The ITT analysis set will be used in the analyses of ORR, progression-free survival (PFS), overall survival (OS), safety, and study drug administration and compliance. The ITT analysis set will be the primary analysis set for all the efficacy variables.

Duration of response (DOR) and time-to-response (TTR) will be analyzed based on all ITT subjects who achieve a CR or PR (including MR for subjects with WM). Lymph node response rate (LNR) will be analyzed based on all ITT subjects who have both baseline and  $\geq 1$  evaluable post-baseline tumor assessments.

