### 6.2. Statistical Hypothesis for the Primary Efficacy Endpoint

The study will test the hypothesis that ORR is  $\geq 39\%$  (i.e.  $\geq \sim 40\%$ ) against the null hypothesis that it is  $\leq 20\%$ .

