### **6.3. Analysis of the Primary Efficacy Endpoint**

The ORR and 95% CI will be presented along with the corresponding p-value from the exact binomial test. The number and proportion of subjects who were evaluated as CR, PR, SD, PD, NE, and ND will also be tabulated.

The primary analysis for ORR will be conducted in the ITT set based on the IRC assessments. The investigator assessments will also be summarized. Both investigator and IRC assessments for tumor response will be listed in detail including site of lesion, date and method of evaluation, bidirectional measures and sum of the products of the perpendicular diameters of measurable index lesions (SPD). Summaries will also be provided for response at each visit separately when tumor assessment is available.

Agreement in best overall response between IRC and investigator assessments will be summarized.

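### The printed Stage 1 false-stop (0.091) holds at a 39% response rate, but power above 0.90 for 100 subjects holds at 40% and not at 39%

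*SAP*

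**What the plan says.** Sections 1.3 and 6.2 set the null at an ORR of 20% or less and the alternative at 39% or more, with about 40% in brackets. Section 1.3 cites Simon's optimal two-stage design and states that "a sample size of 100 subjects has power $>$ 0.90 to achieve a 1-sided significance level of $<$ 0.005". Section 1.2 gives the same level: "to achieve a 1-sided significance level of 0.005 and will provide an ample safety database".

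Section 2.1 continues to Stage 2 if at least 9 of 31 Stage 1 subjects respond, and describes this look as futility only. It prints a probability of 0.151 of wrongly proceeding under the null, and says that the probability of "erroneously discontinuing the study is 0.091 under the alternative hypothesis".

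Section 1.3 also reports the actual enrolment: "A total of 125 subjects have been enrolled into this study and this will provide" power above 0.90. For the primary analysis, Section 6.3 says: "The ORR and 95% CI will be presented along with the corresponding p-value from the exact binomial test". It repeats neither the 0.005 level nor a responder count. Section 3.7 sets a default of 2-sided 0.05 unless otherwise specified.

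**The concern.** The false-stop probability and the overall power describe one design under one alternative hypothesis, so they should be computed at the same response rate. The rounding from 39% to about 40% leaves room for each to be computed at a different end, and the figures suggest that this happened. A reader then cannot tell which rate the 100 subjects were powered to detect.

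The credibility of the design statement is at stake, not the size of the trial. A smaller matter goes with it. The power for 125 subjects can only be checked once a rejection basis is chosen, and Section 6.3, where the test is named, does not carry the significance level.

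**Working it through.** **Inputs.** Null rate 0.20 and alternative 0.39 or 0.40 (Sections 1.3, 6.2); Stage 1 size 31, continue at 9 or more (Section 2.1); Stage 2 size 69, total 100 (Section 2.2); 125 enrolled (Section 1.3); 1-sided level below 0.005 (Section 1.3; 0.005 in Section 1.2).

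**Step 1: the Stage 1 figures.**
- False-go: P(X ≥ 9 | n=31, p=0.20) = 0.1508. The SAP prints 0.151, so the model is the right one.
- False-stop: P(X ≤ 8 | n=31, p) = 0.0908 at p=0.39 and 0.0738 at p=0.40. The SAP prints 0.091, which is the 39% value.

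**Step 2: a ceiling on power.** A subject group that fails Stage 1 cannot reject later, so overall power cannot exceed 1 − false-stop. At 39% this is 1 − 0.0908 = 0.909, whatever the final cut-off or total size.

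**Step 3: overall type I error and power for 100 subjects.** For final cut-off r, the rejection probability is the sum over x = 9 to 31 of P(X₁ = x) × P(X₂ ≥ r − x), with X₁ ~ Bin(31, p) and X₂ ~ Bin(69, p).

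| Cut-off | Type I error (20%) | Power at 39% | Power at 40% |
|---|---|---|---|
| ≥29/100 | 0.0130 | 0.903 | 0.922 |
| ≥30/100 | 0.0078 | 0.897 | 0.919 |
| ≥31/100 | 0.0045 | 0.887 | 0.912 |
| ≥32/100 | 0.0024 | 0.872 | 0.902 |

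The first two-stage cut-off below 0.005 is 31. At 39% the cut-offs with power above 0.90 have too large a type I error, and those with type I error below 0.005 have too little power. The shortfall from 0.90 is 0.900 − 0.887 = 0.013 with the two-stage count. The single-stage exact test, which ignores the gate, gives p = 0.0061 for 31/100 and 0.0031 for 32/100, so it needs 32. The shortfall is then 0.900 − 0.872 = 0.028.

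**Step 4: where the power claim becomes true.** With 31/100, power is 0.8979 at 39.4% and 0.9004 at 39.5%. At 39.5% the false-stop is already 0.082, so no single rate reproduces both printed figures.

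**Step 5: 125 subjects**, same gate, second stage 125 − 31 = 94.

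| Cut-off | Two-stage type I error | Single-stage exact p | Power at 39% | Power at 40% |
|---|---|---|---|---|
| ≥37/125 | 0.0045 | 0.0068 | 0.903 | 0.923 |
| ≥38/125 | 0.0026 | 0.0038 | 0.899 | 0.920 |

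The two bases give different decisions at 125 only for exactly 37 responders.

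**The case against.** The best defence is that Section 1.3 itself brackets about 40% beside 39%. At 40% the power claim is true under either cut-off (0.912 or 0.902), so the sample size calculation has not failed. That stands as far as power goes, but it makes the false-stop wrong (0.074, not 0.091). Choosing 39% repairs the false-stop and breaks the power claim. The larger shortfall of 2.8 points also depends on the single-stage cut-off, whereas Section 1.3 rests its power on the two-stage design. On that basis the gap is 1.3 points.

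Several stronger readings are tempting, and the SAP does not support them.
- **That the trial is underpowered.** The 125 enrolled bring power to about 0.90 at 39% and about 0.92 at 40%.
- **That the primary decision rule is undefined because no responder count is printed.** The null rate, the 1-sided 0.005 level, the exact binomial test, the ITT set and the IRC assessment are all stated. The plain reading of Section 6.3 is the single-stage test, which gives at least 38 of 125. The count follows once the ITT size is known.
- **That ignoring the Stage 1 gate inflates type I error.** A futility-only look can only lower it: 0.0026 with the gate against 0.0038 without, at 38/125.
- **That Section 2.2 contradicts the 125 enrolled.** It says that "it is planned that 69 subjects will be enrolled to achieve the total intended sample size of 100 subjects". That is a statement of plan, and the same section times the final analysis to all enrolled subjects.

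**Conclusion.** The point holds as a minor inconsistency. Two operating characteristics printed for one design and one alternative cannot both be right at the same response rate: 0.091 belongs to 39%, and power above 0.90 for 100 subjects needs about 39.5% or more with the two-stage boundary. The error is 1.3 points of power at 39% (2.8 with the single-stage cut-off) or, at 40%, 0.091 − 0.074 = 0.017 in the false-stop. The statement for 125 is right at 40% on either basis and at 39% with the two-stage count. At 39% with the single-stage test it is 0.899, so about 0.90 rather than above it.

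These results assume that one response outcome serves both looks (Section 2.1 uses investigator assessment at Stage 1, while the final test uses IRC), that the gate of 9/31 is kept when the total is 125, and that all 125 enrolled are in the ITT set. Section 3.1.1 limits that set to subjects with at least one dose, so the final count could shift if some enrolled subjects were not treated.

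**What to change.** Name one alternative rate in Sections 1.3, 2.1 and 6.2, name one final rejection basis, and quote every figure on that pair:

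| Basis | Rate | False-stop | Power, 100 | Power, 125 |
|---|---|---|---|---|
| Two-stage boundary (≥31/100; ≥37/125) | 39% | 0.091 | 0.887 | 0.903 |
| Two-stage boundary (≥31/100; ≥37/125) | 40% | 0.074 | 0.912 | 0.923 |
| Single-stage exact binomial (≥32/100; ≥38/125) | 39% | 0.091 | 0.872 | 0.899 |
| Single-stage exact binomial (≥32/100; ≥38/125) | 40% | 0.074 | 0.902 | 0.920 |

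If the third row is chosen, the power statement for 125 should read about 0.90. As a secondary clarification, repeat the 1-sided 0.005 level of Sections 1.2 and 1.3 in Section 6.3, so that nobody applies the Section 3.7 default. Under that default 35 of 125 would pass (one-sided tail 0.0198, below 0.025).

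The cost is SAP wording only. The number of subjects, the stage sizes and the Stage 1 rule stay as they are.
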